We enrolled adult participants who are ≥ 18 years old and were admitted to the Pain Management Program at The Menninger Clinic in Houston, Texas. Patients presented with multiple and myriad chronic pain concerns, such as: testicular pain, vaginal floor pain, chronic regional pain syndrome (CRPS) of the foot, headache (migraine, cluster), lower back pain (e.g., L4-L5 herniation), and upper back pain (post cervical fusion). Additionally, each patient presented with significant co-morbid psychiatric burden of illness, such as multiple axis I disorders (e.g. major depressive disorder, anxiety-spectrum disorders, and the like) with maladaptive personality traits (including formal diagnoses of personality disorders), severe and chronic suicidal ideation (and attempts) as well as multiple previous outpatient providers and hospitalizations. The Pain Management Program itself did not specialize in the treatment of a particular chronic pain etiology, and as such, there was significant heterogeneity in terms of pain syndromes as well as co-morbid psychiatric concerns. For this study, CP was defined as pain lasting over 6 months or with duration longer than expected for its natural course of recovery and with a self-reported average intensity of 4 / 10 or greater within the past 24 hours. Women were eligible following a confirmed negative pregnancy test (which is conducted within 24 hours of admission to the hospital as part of standard clinical care). Exclusion criteria were active psychosis and cognitive impairment. Patients with preexisting irritation, cuts, or lesions where the tDCS electrodes were to be placed (i.e., the forehead) were excluded from the study. Participants had to have been free of unstable medical conditions, or conditions that may increase the risk of seizure, such as uncontrolled epilepsy. Patients with a history of severe cranial trauma with alteration of the cranial anatomy or metallic intracranial implants were excluded. Potential participants with known sensitivity to Lidocaine 4% were not eligible. Patients with documented Raynaud's phenomenon were not eligible given potential safety concerns (Birnie et al., 2012) associated with this condition and one of the outcome measures (Cold Pressor Test, discussed below). Recruitment of potential participants was limited to patients admitted to the Pain Management Program at The Menninger Clinic; they were contacted through direct verbal communication by a member of the research team.

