Prior to simulation participants cleaned the skin over their foreheads with single use alcohol preps (70% isopropyl; Covidien 2011) and allowed it to dry. This reduced the likelihood that other chemicals (e.g. lotions, makeup, etc.) would interfere with stimulation. To reduce the likelihood of irritation related to electrical stimulation, a low dose (1/8 of an inch) topical lidocaine (4%) cream was then applied to the skin. Skin pretreatment with a topical anesthetic has demonstrated benefit in reducing mild irritation associated with both active and sham tDCS conditions (Guarienti et al 2014). Although side-effects from lidocaine (4%) cream are rare (Baumann et al 2010, Oni et al 2010), patient safety was assured by waiting for a 3-minute period where participants are asked to report any potential discomfort associated with the use of lidocaine. The trial was discontinued if a participant responded affirmatively. To minimize the likelihood of skin irritation after each tDCS session (Naylor et al 2014), vitamin-E oil (400 Unit; Rugby) was applied to the skin where the electrodes were placed.

Design

The research design was developed in line with requirements for a Phase II, Single Center Device Study as defined by the FDA (United States Food and Drug Administration 2015). In this superiority trial, participants who meet inclusion criteria are randomized (1:1) into a single-blind, 2x12 (group X time) controlled trial. Participants were assigned to one of two groups: active tDCS plus usual care or sham tDCS plus usual care. Only the administering research staff member and PI were aware of tDCS condition applied. Participant's clinical outcomes are collected daily during each day of stimulation as well as weekly for two weeks following the active phase of the trial. Data will be collected for 22 days during the following days: days 1-5, days 8-12, day 15, and day 22.

Procedures

Pre-consent procedures

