Participants completed self-report and performance-based assessments daily during each day of stimulation (prior to the actual stimulation) as well as weekly for two weeks following the active phase of the trial. Data were collected for 22 days during the following days: days 1-5, days 8-12, day 15, and day 22. Self-report assessments are collected via Chronic Pain Tracker version 3.6, an iPad interfaced application (See Figures 3 and 4; (Chronic Stimulation 2015). Participants were asked to rate their experience during the past 24 hours across the following domains: pain intensity (on a 0-10 visual analogue scale; outcome measure for primary aim), pain triggers (from a list of 10 common pain triggers; outcome measure for primary aim), pain description (using descriptors from the McGill Pain Questionnaire, (Melzack 1987), sleep history (including total duration, time to sleep onset, use of sleep aids, subjective rating of sleep quality [0-10 point Likert-scale]; outcome measure for secondary aim), and physical activity level (on a 0-10 point Likert-scale from light to heavy; outcome measure for secondary aim).

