After each active or sham tDCS session a checklist of potential side-effects was used (Brunoni et al 2011). As suggested by Brunoni (2011), participants were instructed to describe any discomfort they may experience. The intensity of the acknowledged discomfort was rated by participants using a scale with a range of 0 to 3 points. Displayed in ascending levels, the scale measures the absence of a potential side-effect, and escalates in intensity (0 = Absent, 1 = Mild, 2 = Moderate, and 3 = Severe). The researcher administrating active or sham tDCS further evaluated each potential side effect endorsed by participants. Researchers ask the participant to indicate the degree to which they consider the discomfort to be related to tDCS through an escalating scale ranging from 0 to 4 points (0 = None, 1 = Remote, 2 = Possibly, 3 = Probable, and 4 = Definite). Additionally, the researcher also rated the degree to which he/she considers the discomfort to be related to tDCS using the same scale. See table 3. Given that there is evidence to suggest that participants can distinguish between active and sham tDCS (O'Connell et al., 2012) and this may result in an expectation effect, participants were formally assessed

after the last outcomes assessment about their perception of which arm of the study they were assigned.

Missed Sessions and Early Termination of Participation

Participants who for any reason missed a scheduled brain stimulation session or assessment were given the opportunity to make up the session/assessment on the following day (including weekends as necessary). Participants were allowed to withdraw from the study for any reason without affecting their clinical care.

Data Management Procedures

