Finally, real-time standardized outcome assessments were completed by each inpatient during admission, every two weeks during the hospitalization as well as upon discharge (Allen et al 2009, Confer et al 2015). The outcomes assessment protocol included standardized measures of psychopathology, functioning and wellbeing. All of the selected measures are used in clinical practice and research settings; each has sound psychometric properties with adequate sensitive to change. Patients and clinicians were provided reports of the assessments within 24 hours of completing them. Ongoing assessment of treatment outcomes allowed for modification of treatment plans (including adjustments to pharmacologic regimens), thus allowing for personalization of evidence-based treatments and improving the likelihood of treatment response.

Statistical Analyses

Statistical analysis were to be conducted using a 2X12 [tDCS group X time] mixed generalized linear modeling approach with CPT duration of submersion as the primary dependent measures. Secondary analysis were to employ hierarchical linear modeling (HLM) to examine changes in numerical ratings of self-reported pain, activity, and sleep disturbance, while controlling for mood (time-series). Had any of the outcome variables been non-normally distributed, each were to be log-transformed before applying the formal linear modeling analyses. All analyses were to be conducted using SAS/STAT software, Version 9.3 of the SAS System for Microsoft Windows, Cary, NC, USA.

Note, no formal analyses were conducted. Given the premature termination of the clinical program, the limited sample size of participants completing the study, the heterogeneity of CP etiology and psychiatric comorbidity among participants, as well as variable and personalized interventions delivered as a part of the clinical care participants received, the data collected would have been grossly underpowered to provide meaningful results.

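### No structured side-effect collection is stated after the day 12 session, and the checklist has no recall period for effects arising between sessions

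*Combined protocol and SAP*

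**What the plan says.** Under Assessment Procedures, the timing of the side-effect form is given once: "After each active or sham tDCS session a checklist of potential side-effects was used". The prompt is open: "participants were instructed to describe any discomfort they may experience". Each endorsed effect is graded 0 to 3 for intensity. Participant and researcher each rate its relation to stimulation from 0 to 4. No recall period, onset date or resolution date is mentioned.

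The assessment calendar in the same section reads: "Data were collected for 22 days during the following days: days 1-5, days 8-12, day 15, and day 22". Assessments are made before stimulation on session days, "as well as weekly for two weeks following the active phase of the trial". The self-report does have a recall period: "Participants were asked to rate their experience during the past 24 hours across the following domains". The domains are pain intensity, triggers and description, sleep, and physical activity. The cold pressor task is the performance measure. None of these is a side-effect item.

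One other harm question appears, under Pre- and post-stimulation skin treatment: a 3-minute wait before stimulation in which participants are asked about discomfort from the lidocaine cream.

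**The concern.** A form given only after a session stops when the sessions stop. Two visits follow the last session, and they exist to see what lasts after stimulation. As written, they ask that question about pain, sleep and activity but not about side effects. Within the stimulation weeks, the efficacy ratings have a defined look-back and the side-effect form does not. A participant may or may not mention something that began the evening after the previous session and had faded by the next.

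What is at stake is what the trial can report on tolerability. It could describe discomfort reported at the end of each session, by arm. It could not say, by arm and from a structured source, whether effects appeared later, how long they lasted or whether they had resolved by day 22. A low count of delayed effects would be hard to interpret, because nobody was required to ask.

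**Working it through.** **Reproducing the plan's own figures**
- Sessions (Brain Stimulation Procedures): 5 + 5 = 10.
- Exposure: 10 × 20 min = 200 min, as the plan states.
- Assessment days (Design; Assessment Procedures): 10 session days + days 15 and 22 = 12, which matches the 2×12 design.

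**Coverage of the side-effect checklist**
- Assessment days with a stated checklist: 10 of 12. The two without are days 15 and 22.
- Last stated checklist: day 12. Last study day: day 22. Gap: 22 − 12 = 10 days, that is days 13-22, or 10/22 = 45% of the study days.
- Missed sessions may be made up the next day, weekends included. If the day 12 session moves to day 13, the gap is 22 − 13 = 9 days.

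**Could the past-24-hours self-report fill the gap?**
Assume visits at about the same clock time. The plan puts sessions in the late afternoon but gives no hour for days 15 and 22.
- Consecutive session days: about 24 hours apart, so the interval is covered, but only for pain, sleep and activity.
- Weekend, day 5 to day 8: 3 days, of which the day 8 report covers 1.
- After the last session: 3 days to day 15 and 7 more to day 22. The two reports cover 1 + 1 = 2 of the 10 days, again only for those domains.

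**Could the next checklist fill it?**
For sessions 2-10 it could, since the prompt is open and nothing confines it to the session just ended. But nothing directs it to the earlier interval either. After session 10 there is no next checklist.

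**The case against.** The strongest reply is that harm would not go unnoticed. Under Usual Care in the Pain Management Program, participants have 24-hour nursing with side-effect monitoring, an internist throughout, and an expected stay of 5 weeks. Day 22 falls within a 35-day stay if trial day 1 is no later than stay day 14 (14 + 21 = 35). This stands as protection for the individual patient. It does not supply trial data. That text concerns the usual-care interventions, and Data Management Procedures names the side-effect checklist and cold pressor results as examples of what is entered, without mentioning nursing observations.

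Second, the absence at days 15 and 22 is inferred from silence. That is correct, and part of the source material is not available for review. But the plan sets out in some detail what is collected on assessment days and gives the checklist a specific timing.

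Two stronger readings are tempting. A reader might infer that lidocaine hides the side effects, because the plan says "Skin pretreatment with a topical anesthetic has demonstrated benefit in reducing mild irritation associated with both active and sham tDCS conditions". The checklist comes at least about 3 + 20 = 23 minutes after the cream, but the documents give no duration of action. Any effect would concern local skin sensation, not other effects. Masking of mild irritation is plausible; masking of reporting in general is not supported.

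A reader might also infer that psychiatric worsening is shown to be uncaptured, given the severity of illness described in the eligibility text. The checklist items and the table the plan refers to cannot be seen here. Statistical Analyses plans to adjust for mood over time, which implies repeated mood measurement. The documents do not settle this either way.

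Finally, the program ended early and no formal analyses were done. New forms cannot help past participants, so the point matters for any tolerability statement and for reuse of the design.

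**Conclusion.** The point holds in a limited form. No structured side-effect collection is stated after the day 12 session, which leaves 10 of 22 study days and 2 of 12 assessment days without it. Between sessions, the checklist has no stated recall period, so capture of delayed effects depends on what participants volunteer. Such effects are not systematically collected by arm; saying that they are missed altogether would go too far, because the open prompt and clinical monitoring could each pick some up.

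This rests on two assumptions: that the text lists what is collected on days 15 and 22, and that usual-care observations did not enter the trial database. The conclusion does not depend on how long lidocaine acts, on what items the checklist contains, or on the number of participants. It is a cheap improvement to the harm data and not a flaw in the efficacy comparison.

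**What to change.** - **Days 15 and 22:** give the same checklist, with recall from the previous session or visit, and record onset and resolution dates for anything endorsed. Give it after the pain ratings and the cold pressor task, so that questions about discomfort do not prime those outcomes.
- **Sessions 2-10:** add to the existing post-session form one question on effects since the previous session, with the same dates. Its place after stimulation already keeps it clear of that day's pain assessments.
- **Reporting:** tabulate by arm, separating effects at the session from effects between sessions and after day 12. For data already collected, say that tolerability was assessed by structured checklist only up to the last session.

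This adds one question on 9 occasions and one existing form on 2, 11 in all, at visits that already take place. The cost is a few minutes each time and more reported events in both arms.

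Extracting the clinic's own scores by arm is optional. The plan says that "real-time standardized outcome assessments were completed by each inpatient during admission, every two weeks during the hospitalization as well as upon discharge". These scores are timed from admission and not from study day, so they may not bracket the stimulation period and cannot replace the checklist.

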All participants took part within the Pain Management Program's centralized ("one-stop shopping") model of integrative inpatient clinical services with an expected length of stay of 5 weeks. Diagnosis of CP and pre-existing psychiatric disorders were reviewed by the Pain Management Program prior to admission. Patients received comprehensive psychiatric and medical evaluation as well as personalized treatment. Components of the psychiatric care typically included pharmacologic optimization, including detoxification from opiates and/or other addictive medications as indicated and tolerated. Additionally, given the extended length of the hospitalization, adequate time in treatment allowed for evaluation of adverse polypharmacy, allowing for a reduction in the number, complexity, & dangerousness of patients' medication burden (Madan et al., 2015a). Further, psychotropic medication management targeting both psychiatric and pain symptoms was optimized via pharmacogenomics-informed medical decision based on known interactions between specific psychotropic medications and individually expressed alleles in various transporters, receptors, and enzymes as coded by genes (Madan et al., 2015b). A board-certified internist completed a comprehensive medical evaluation and continues to manage symptoms as indicated throughout the hospitalization. The evaluation included: a physical exam (i.e., skin exam; complete neurologic, cardiovascular and abdominal exams; focused exam of wounds; areas of pain; areas of concern as identified by the patient; and when indicated, pelvic and rectal exams); serum analysis (i.e., complete blood count; thyroid function panel; complete metabolic panel with magnesium and phosphorus; tests for sexually transmitted diseases; tests for vitamin deficiency;

tests of inflammatory biomarkers; and Westergren sedimentation rate (Madan et al., 2016). Of note, these interventions occurred within the context of 24-hour nursing care, resulting in near perfect compliance with prescribed regimen doses and close and objective monitoring of side effects.

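### The only planned models of self-reported pain, activity and sleep adjust for an undefined, probably on-study, mood covariate; if tDCS changes mood, they do not estimate the effect of active versus sham assignment

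*Combined protocol and SAP*

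**What the plan says.** **Statistical Analyses.** The primary model is a group-by-time mixed model over 12 occasions for cold pressor (CPT) submersion time; no mood term is stated for it. For the self-reports: "Secondary analysis were to employ hierarchical linear modeling (HLM) to examine changes in numerical ratings of self-reported pain, activity, and sleep disturbance", and this is to be done "while controlling for mood (time-series"). That is the only analysis stated for those three outcomes. The section gives no mood scale, measurement schedule or lag, and does not say how treatment group enters the secondary models. It ends by noting that no formal analyses were done.

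**Assessment Procedures.** Pain intensity carries a primary-aim label: "pain intensity (on a 0-10 visual analogue scale; outcome measure for primary aim"). On timing: "Participants completed self-report and performance-based assessments daily during each day of stimulation (prior to the actual stimulation"). On the schedule: "Data were collected for 22 days during the following days: days 1-5, days 8-12, day 15, and day 22". The domains that follow "Participants were asked to rate their experience during the past 24 hours across the following domains" do not include mood in the text; the figures showing the app are not available.

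**Usual Care in the Pain Management Program.** The only repeated source that might hold mood is the programme's own battery: "real-time standardized outcome assessments were completed by each inpatient during admission, every two weeks during the hospitalization as well as upon discharge". It covers psychopathology, functioning and wellbeing, and no mood scale is named. The section also says "Patients received comprehensive psychiatric and medical evaluation as well as personalized treatment", but describes no repeated mood score there.

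**Design.** This is a superiority trial with 1:1 randomisation to active or sham stimulation.

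**The concern.** A superiority trial with random allocation is built to estimate the effect of assignment. Adjusting for a variable measured after treatment starts can break that. If tDCS changes mood, directly or because less pain lifts mood, holding mood fixed takes out the part of the treatment effect that is shared with mood. Where mood and the outcome also share other causes, it adds further bias.

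The documents make a mood effect plausible without asserting it. Stimulation is prefrontal (Brain Stimulation Procedures), and major depressive and anxiety-spectrum disorders are among the comorbidities listed for the enrolled patients.

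At stake is the arm comparison for pain, activity and sleep, including one outcome tied to the primary aim. If active stimulation improves mood, a real effect would be understated. Whichever reading is right, an analyst following the plan would have to invent the covariate.

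**Working it through.** **1. The plan's own figure.** With f = .25, correlation ρ = .5, α = .05 and m = 12 occasions (from the 2x12 design), a between-groups repeated-measures F test has λ = f²Nm / (1 + (m − 1)ρ). At N = 70, λ = .0625 × 70 × 12 / 6.5 = 8.08 on 1 and 68 df, which gives power .800. The stated 70 reproduces. It does not bear on the mood question; it supplies the reference effect d = .51 and 35 per arm.

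**2. Which mood values precede treatment.** Assessments come before each session. The schedule has 5 + 5 + 1 + 1 = 12 occasions. Only Day 1 precedes all stimulation; the other 11 follow at least one session.

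**3. What the two-weekly battery could supply.** Assume scores 14 and 28 days after admission. If Day 1 falls k days after admission, they land on study days 15 − k and 29 − k. For k = 1 to 6, one falls in the 22-day window (study days 9 to 14). For k = 7 to 13, two do (for example days 8 and 22). All come after the Day 1 session.

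**4. Closed form, mood scored at every occasion.** Adjusted effect = .51 − r × d_mood, where d_mood is the effect of assignment on mood in SD and r the mood-pain correlation within arm. Neither figure is in the documents; both are assumed.
- d_mood .2, r .3: .51 − .06 = .45
- d_mood .4, r .4: .51 − .16 = .35
- d_mood .5, r .6: .51 − .30 = .21
- d_mood 0: .51, no bias

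If mood changes only because pain falls, d_mood = r × .51 and the adjusted effect is .51(1 − r²): .46, .43 and .33 for r = .3, .4 and .6.

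**5. Simulation on the trial's schedule.** Setup: 35 per arm; within-person correlation .5 for pain and for mood; effects assumed to be zero on Day 1, rising linearly to full size at Day 12, then held; random-intercept model with occasion terms, group, and group × ramp, the last being tested. There were 2000 replicates per case without mood and with mood at all 12 occasions, and 1500 for the sparse cases, where an admission score and the later battery scores are carried forward.

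| Mood covariate | d_mood .2, r .3 | d_mood .4, r .4 | d_mood .5, r .6 |
|---|---|---|---|
| None | .51 (98%) | .51 (98%) | .51 (97%) |
| All 12 occasions | .45 (95%) | .35 to .36 (83%) | .21 (49%) |
| Two scores (days 8, 22) | .49 (96%) | .47 (93%) | .43 (87%) |
| One score (day 9) | .50 (96%) | .48 (94%) | .45 (91%) |

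Entries are estimate (power). Repeating the sparse cases gave .46 to .47 and .42 to .45 for the middle and high columns, with power 86% to 92%. These powers test group × ramp and are not comparable with the plan's .80. With no mood effect, the estimate was .510 both with and without mood.

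**6. Shared causes.** In a separate simulation with mood at all occasions, an effect of .3 on mood and a causal mood-to-pain slope of .4 took .51 to .39. Adding an unmeasured common cause of mood and pain (loading .5) took it to .13. With that common cause and no mood-to-pain path, it went to .25. So the distortion is not limited to removing a mediated part.

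**The case against.** The strongest objection is about reading. The parenthesis closes a sentence about examining changes by hierarchical modelling, so it may describe that analysis rather than the covariate. If a baseline mood score is meant, the criticism of the estimand falls away and only an undefined covariate remains. This stands, and it is why the point is conditional.

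Second, a reader might infer from the highest case that power would collapse to about 49%. The documents do not support that. It needs a mood score at all 12 occasions, which the text does not describe, and a mood effect about as large as the whole planned pain effect. On the only repeated source described, the same assumptions leave power at about 86% or more. A daily mood item in the unseen app figures cannot be excluded, so both ranges are shown. For the same reason, the lack of a mood item in the text does not prove that mood went unrecorded.

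Third, a pain effect independent of mood is a legitimate question in patients with this much psychiatric comorbidity, and the plan does not state the group term of the secondary models. But it does not state that aim either, and such a model should not be the only comparison of randomised arms for these outcomes.

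Fourth, adjustment buys precision. With mood at all 12 occasions it does, but in the three cases of a direct mood effect the smaller standard error did not make up for the lost effect.

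**Conclusion.** The point holds in conditional form. For self-reported pain, activity and sleep, the plan states only a mood-adjusted model and leaves mood undefined. If the covariate is measured on study and tDCS changes mood, the models do not estimate the effect of active versus sham assignment. If either condition fails, that bias does not arise.

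Under the assumed inputs, the loss from .51 ranges from .01 or .02 (low case, one or two battery scores) to .30 (high case, mood at every occasion). The sparse-score results, about .49-.50, .46-.48 and .42-.45, rest on the only repeated source that the text describes. All of these also depend on the assumed ramp.

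A reader might infer that the trial's findings are biased, or that every planned analysis is. Neither follows: no formal analyses were conducted, the primary CPT model states no mood term, and the documents report no effect of tDCS on mood. This is a fault in the plan as a record of intent or a template. It is worth correcting because it reaches a primary-aim outcome and costs little. Confidence is medium, because the phrase is ambiguous.

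**What to change.** Delete the mood clause from the secondary models, and make the active-versus-sham comparison of pain, activity and sleep without any post-randomisation mood covariate. Optionally adjust for one named pre-randomisation mood score, if an admission score exists and can be linked to the research data. Report any model with on-study mood only as a labelled exploratory (mediation) analysis, stating scale, schedule and lag.

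**Cost.** The main change is one of wording and needs no new data. If mood would have been scored at every occasion, the standard error without it is .134, against .128, .123 and .108 with it in the three cases (ratios 1.05, 1.09 and 1.24). With the sparse scores it is essentially unchanged. The optional admission score needs a named scale and a data link that Data Management Procedures does not mention; in the middle case, adjusting for one baseline score left the estimate and standard error unchanged (.513 and .134).
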